MRI: Magnetic Resonance Imaging; a-PET: Amyloid PET; CSF: Cerebrospinal fluid; EKG: Electrocardiogram; exc.: except; IGE: Investigator Global Evaluation; NPB: Neuropsychological battery; FV: final visit; Vc: Vaccination; Sc: Safety control; Int: Interim analysis; T: Telephone call; RR: respiratory rate; T^o: body temperature

[†]The Screening Visit (V0) should be performed in 4 separate days:

¹Day 1 of V0 (V0a):

- Signature of informed consent and verification of inclusion and exclusion criteria; medical history, vital signs, physical and neurological exam, neuropsychological battery, EKG, concomitant medication for AD and other diseases and delivery of Patient Card and Patient Diary; the scanned EKG must be sent to the Medical Advisor and no further assessments can be made to the subject until the approval is received at the center.
- If the patient meets all neuropsychological criteria, once the EKG has been approved by the Medical Advisor, the Day 2 of V0 (V0b) can be scheduled

²Day 2 of V0 (V0b):

- Urine analysis and blood sample extraction (for hemogram, biochemistry and biological activity)
- If no abnormal findings are found in the blood and urine tests, the Day 3 of V0 (V0c) can be scheduled.

³Day 3 of V0 (V0c):

- Magnetic Resonance Imaging
- Once the MRI has been approved by the MRI Central Reader, the Day 4 of V0 (V0d) can be scheduled

⁴Day 4 of V0 (V0d):

- a-PET
- Once the a-PET has been approved by the a-PET Central Reader, the patient can be randomized and the first day of V1 can be scheduled (a minimum of 4 days later, so that the appropriate material for CSF extraction and the IMP can be received at the center).

* The Inclusion Visit (V1) should be performed in 2 separate days; the vaccination should take place at least 3 days after the CSF extraction, **or the time needed until resolution of any AE occurring after the CSF extraction, whichever is longer** (to avoid interference with the assessment of AEs related to the vaccination), **with a maximum of 10 days after the urine and blood sample extraction:**

- Day 1 of V1 (V1a):
 - Urine analysis, blood sample extraction (for ApoE genotyping, hemogram, biochemistry and biological activity) and CSF collection
- Day 2 of V1 (V1b):
 - Physical and neurological exam, neuropsychological battery and IGE, quality of life, vital signs (before vaccination), vaccination, vital signs (after vaccination), concomitant medication and AEs.

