7.2 Summary of Primary Safety Outcome

7.2.1 Adverse Events

Adverse events will be classified as Treatment-Emergent AEs (TEAEs) or non-Treatment-Emergent AEs (non-TEAEs), based on the comparison of the AE onset date/time with the start date/time of study treatment.

- A TEAE will be defined as an AE which starts or worsens in severity during or after the first administration of study treatment.
- A non-TEAE will be defined as an AE which starts or worsens in severity prior to the start of the first administration of study treatment.

The following algorithm will be used to identify the treatment group under which each AE will be summarized:

For SAESIs:

- AEs that start or worsen in severity at any time after a patient's first dose of ABvac40 will be associated with the ABvac40 treatment group.
- AEs that start or worsen in severity after first dose of Placebo, but before first dose of ABvac40, will be associated with the Placebo treatment group

For non-SAESIs:

- For patients randomised to the ABvac40 arm Part A / Placebo+Booster arm Part B treatment sequence:
 - AEs that start or worsen in severity at any time during or after a patient's first dose of study drug in part A and prior to their booster ABvac40 vaccination will be associated with the treatment received at their last injection prior to the AE.
 - AEs that start or worsen in severity during or after a patient's booster ABvac40 vaccination will be associated with the ABvac40 treatment group.
- For patients randomised to the Placebo arm Part A / ABvac40 arm Part B treatment sequence:
 - AEs will be associated with the treatment received at their last injection prior to the AE.

For the purposes of classifying AEs as treatment emergent and to assign treatment groups, partial AE start and end dates will be imputed to allow comparison with the study treatment date start and end dates. Section 9.1.1 below presents the imputation rules. Note, the imputed dates will be used for classification purposes and treatment group assignment purposes only and the original partial AE dates will be presented in data listings.

An overall summary of AEs will be presented by treatment group, by providing counts and percentages of patients with any: TEAE, non-TEAE, Treatment related TEAEs, TEAE leading to treatment discontinuation, TEAEs leading to death, Treatment-Emergent Serious AE (TESAE), Treatment-

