9 APPENDICES

9.1 Imputation rules

9.1.1 AE date imputation

The following rules will be applied to impute AE start/end dates when partial AE start/end dates have been recorded. The imputed dates will be used for the determination of TEAEs only. The original partial AE dates will be presented in data listings.

AE start date imputation:

AE start date imputation will be based on a comparison of the partial AE start date and the treatment start date. [Table 2-1](#) presents the notation that will be used to describe the rules for imputation of partial AE start dates.

Table 2-1 Notation for imputation of partial AE start dates

	Year	Month	Day
Partial AE start date	YYYY	MON	Not used
Study treatment start date	TRTY	TRTM	Not used

[Table 2-2](#) presents a matrix of rules for the imputation of AE start dates.

Table 2-2 AE start date imputation

	MON MISSING	MON < TRTM	MON = TRTM	MON > TRTM
YYYY MISSING	NULL Uncertain	NULL Uncertain	NULL Uncertain	NULL Uncertain
YYYY < TRTY	(D) = 01JULYYYY Before Treatment Start	(C) = 15MONYYYY Before Treatment Start	(C) = 15MONYYYY Before Treatment Start	(C) = 15MONYYYY Before Treatment Start
YYYY = TRTY	(B) = TRTSTD+1 Uncertain	(C) = 15MONYYYY Before Treatment Start	(A) = TRTSTD+1 Uncertain	(A) = 01MONYYYY After Treatment Start
YYYY > TRTY	E = 01JANYYYY After Treatment Start	(A) = 01MONYYYY After Treatment Start	(A) = 01MONYYYY After Treatment Start	(A) = 01MONYYYY After Treatment Start
Before Treatment Start	Partial indicates date prior to Treatment Start Date			
After Treatment Start	Partial indicates date after Treatment Start Date			
Uncertain	Partial insufficient to determine relationship to Treatment Start Date			
LEGEND:				

MON MISSING	MON < TRTM	MON = TRTM	MON > TRTM
NULL	No imputation		
(A)	Max(01MONYYYY,TRTSTD+1)		
(B)	TRTSTD+1		
(C)	15MONYYYY		
(D)	01JULYYYY		
(E)	01JANYYYY		

1. If the AE start date year value is missing, the date uncertainty is too high to impute a rational date. Therefore, if the AE year value is missing, the imputed AE start date is set to NULL (i.e. no imputation).
2. If the AE start date year value is less than the treatment start date year value, the AE started before treatment. Therefore:
 - a. if the AE year is less than the treatment year and the AE month is missing, the imputed AE start date is set to the mid-year point (01JulYYYY).

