 - b. else, if the AE year is less than the treatment year and the AE month is not missing, the imputed AE start date is set to the mid-month point (15MONYYYY).
3. If the AE start date year value is greater than the treatment start date year value, the AE started after treatment. Therefore:
 - a. if the AE year is greater than the treatment year and the AE month is missing, the imputed AE start date is set to the year start point (01JanYYYY).
 - b. else, if the AE year is greater than the treatment year and the AE month is not missing, the imputed AE start date is set to the month start point (01MONYYYY).
4. If the AE start date year value is equal to the treatment start date year value:
 - a. and the AE month is missing or the AE month is equal to the treatment start month, the imputed AE start date is set to one day after treatment start.
 - b. else, if the AE month is less than the treatment start month, the imputed AE start date is set to the mid-month point (15MONYYYY).
 - c. else, if the AE month is greater than the treatment start month, the imputed AE start date is set to the start month point (01MONYYYY).

Imputed AE date flag

If the year of the imputed date is not equal to YYYY then imputed date flag = Y, else if month of the imputed date is not equal to MON then imputed date flag = M, else if day of the imputed date is not equal to day of original date then imputed date flag = D, else imputed date flag = null.

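### The AE start-date imputation in SAP 9.1.1 ignores the recorded end date, so an event that resolved before the first dose can be counted as treatment-emergent

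*SAP*

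**What the plan says.** SAP 9.1.1 opens by promising rules for partial AE start and end dates, and SAP 7.2.1 likewise says both will be imputed. Only start-date rules follow. Their basis is stated: "AE start date imputation will be based on a comparison of the partial AE start date and the treatment start date". Under rule 4a, for a start in the year of the first dose, where "the AE month is equal to the treatment start month, the imputed AE start date is set to one day after treatment start"; a start with no month is treated the same way. Table 2-2 gives the same result and labels those cells uncertain. Under rule 1, a start with no year is left NULL.

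SAP 7.2.1 then classes each AE "based on the comparison of the AE onset date/time with the start date/time of study treatment", and states: "A TEAE will be defined as an AE which starts or worsens in severity during or after the first administration of study treatment". Onset alone decides the class.

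Other relevant text:

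- AEs are collected from signing of the consent form (Protocol 8.2.1), and screening may begin up to 60 days before treatment (Protocol 4.9.1.1).
- A lumbar puncture is done on the first day of V1. The first injection follows at least 3 days later, "or the time needed until resolution of any AE occurring after the CSF extraction, whichever is longer", and at most 10 days after the blood and urine samples (Protocol 4.2.1).
- The date of resolution is a required eCRF item (Protocol 8.3.8).
- For medications, SAP 9.1.2 does use a complete end date to resolve a missing start.
- SAP 9.1.1 restricts imputed AE dates to deciding TEAE status; SAP 7.2.1 also uses them to assign the treatment group.

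**The concern.** Sending an uncertain start to the treatment-emergent side is a sound cautious convention. It stops being sound when a recorded end date removes the uncertainty. An event that was over before the first injection cannot have started the day after it, yet rule 4a gives it that date.

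The design foresees such events. Any AE from the lumbar puncture is meant to have resolved before the first injection, and the protocol separates the two days so that procedural events do not confuse the assessment of vaccine reactions. For partial dates, rule 4a undoes that separation. AE frequency is the primary safety variable, so its classification rule should not contradict a date already in the database.

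**Working it through.** The plan states no figure for this rule, so there is none to reproduce. The rule was applied as written, first to one case and then to a range of dates.

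**Worked case (invented dates within the recruitment period).** First dose 20 Mar 2019; AE ended 14 Mar 2019.

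- Start recorded as Mar 2019, day missing: same year and month, so imputed start = 20 Mar + 1 = 21 Mar 2019. That is 7 days after the event ended. Class: TEAE.
- Start recorded as 2019 only: again 21 Mar 2019, TEAE.
- Year missing: NULL, with no class stated.

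**How often the rule misfires on a partial-date record.** Assumptions: first doses fall evenly on the 607 days from 1 Feb 2018 to 30 Sep 2019 (334 in 2018 plus 273 in 2019), the planned first-patient-in and last-patient-in months. The AE starts k days before the first dose, with k uniform on 1 to W, and ends before it.

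*Day missing.* The rule misfires when start and dose share a calendar month, with probability about 1 − k/30.44 for k up to 30 and about zero beyond.

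- W = 10: mean k = 5.5, so 1 − 5.5/30.44 = 0.82.
- W = 30: mean k = 15.5, so 1 − 15.5/30.44 = 0.49.
- W = 60: only the first 30 days contribute, so 30 × 0.49/60 = 0.25.

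*Day and month missing.* The rule misfires when start and dose share a calendar year.

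- W = 10: the start falls in the previous year for k of the 607 dose dates, so 1 − 5.5/607 = 0.99.
- W = 30: 1 − 15.5/607 = 0.97.
- W = 60: 30.5/607 = 0.050 for doses early in 2019, plus (435/60)/607 = 0.012 for doses in February 2018 whose event began in 2017 (435 is the sum of k − 31 over k = 32 to 60). So 1 − 0.062 = 0.94.

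A full enumeration agrees:

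| Window before first dose | Day missing | Day and month missing | With an end-date check |
|---|---|---|---|
| 10 days | 81.9% | 99.1% | 0% |
| 30 days | 49.0% | 97.4% | 0% |
| 60 days | 24.5% | 93.8% | 0% |

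The last column assumes a complete end date. Complete start dates, and partial starts in a known earlier month or year, are classed correctly as they stand.

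**Effect per misclassified patient.** In one row of a table, one extra patient moves the percentage by 100/60 = 1.7 points in an arm of 60, or 100/120 = 0.8 points if all 120 patients enter a pooled denominator. The overall TEAE row moves only if the patient has no other TEAE. If 75% do have one (the Phase I figure for any AE, Protocol Table 1), the expected shift at n = 60 is 0.25 × 1.7 = 0.4 points.

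**Effect on the arm comparison.** If a spurious TEAE occurs with probability q in each arm, independently of true TEAEs, a true rate p is counted as p + q(1 − p), and the difference between arms is multiplied by 1 − q. As an illustration, one affected patient per arm of 60 gives q = 1/60 and a factor of 59/60 = 0.983.

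**The case against.** The strongest reply is that this will hardly ever matter. The default is cautious and blind to arm. Post-puncture events are closely watched because their resolution decides when vaccination may go ahead; onset and resolution dates are required items; patients keep a diary; and missing data are queried (Protocol 8.2.7, 8.3.8, 11.3.4, 11.3.5). The primary safety analysis is descriptive with no numerical threshold, and tables count patients, not events. All of this stands, and it limits the size of the problem. None of it supplies the missing check.

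Three stronger readings are tempting but unsupported.

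- *Unknown-year events vanish from every AE table.* The SAP gives them no class or treatment column, and the AE summaries in 7.2.1 are built on TEAE and non-TEAE. But it never says they are dropped. They remain in the listings, and a program that sorts a missing date as earliest would place them among the non-TEAEs. The gap is an unstated rule, not a demonstrated loss.
- *Most pre-dose events are misclassified.* For an event starting on the puncture day with a month-only date, the share is 1 − 3/30.4 = 90% at a 3-day gap and 1 − 10/30.4 = 67% at a 10-day gap. That is one narrow case; over the 60-day window, the day-missing share is 25%.
- *An event can be both TEAE and non-TEAE.* The second definition reads "A non-TEAE will be defined as an AE which starts or worsens in severity prior to the start of the first administration of study treatment", so on paper the two overlap. But classification is by onset, and Protocol 8.2.4 to 8.2.6 record a worsening examination, EKG or MRI finding as its own AE. This is loose wording and unrelated to imputation.

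**Conclusion.** The point holds for a defined set of records: AEs with a partial start in the first-dose year, month missing or equal to the first-dose month, and an end date before the first dose. For these, SAP 9.1.1 yields a start after the end and the wrong class. Conditional on a partial date, 25% to 82% of pre-dose-resolved events are affected when the day is missing and 94% to 99% when the month is missing too, under the uniform-onset assumption.

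The documents do not give the frequency of partial dates, so the number of affected records cannot be computed; it is probably small. The expected effect is a slight inflation of TEAE counts in both arms. A reader might infer a material bias in the vaccine-placebo comparison. The documents do not support that: the rule ignores arm, and the illustrative shrinkage is under 2% of the difference. This is a small specification error worth correcting because the correction is almost free.

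**What to change.** Add two sentences to SAP 9.1.1: an AE whose end date is before the first dose (complete, or partial but certainly earlier) is non-TEAE; and an imputed start may not be later than the end date.

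Make three secondary clarifications:

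- State the AE end-date imputation rule that 9.1.1 and 7.2.1 announce.
- State how unknown-year events are classed: non-TEAE if the end date or the visit of first recording is before the first dose, otherwise TEAE. Take the treatment column from the last injection before the visit of first recording, leaving the 7.2.1 rules for special-interest and post-booster events in place.
- Reconcile the restriction in 9.1.1 to TEAE determination with the use of imputed dates in 7.2.1 for treatment-group assignment.

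The cost is a few sentences and a few lines of code. No new data are needed, since the resolution date is already collected. The cautious default stays for every event whose timing is truly uncertain.

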9.1.2 Prior and concomitant medication date imputation

The following rules will be applied to impute medication start/end dates when partial medication start/end dates have been recorded. The imputed dates will be used to distinguish between prior and concomitant medications only. The original partial medication dates will be presented in data listings.

- The missing day of start date of a medication will be set to the first day of the month that the medication was taken.
- The missing day of end date of a medication will be set to the last day of the month of the occurrence.
- If the start date of a medication is missing both the day and month, the medication start date will be set to January 1 of the year of medication start.
- If the end date of a medication is missing both the day and month, the date will be set to December 31 of the year of occurrence.
- If the start date of a medication is null and the end date is not a complete date, then the start date will be set to the date of the first study visit.
- If the start date of a medication is null and the end date is a complete date
 - and the end date is after the date of the first study visit then the start date will be set to the date of the first study visit.
 - otherwise the start date will be set to the end date of the medication.
- If the end date of a medication is null and the start date is not a complete date, then the end date will be set to the date of the last study visit.
- If the end date of a medication is null and the start date is a complete date
 - and the start date is prior to the date of the last study visit then the end date will be set to the date of the last study visit.
 - otherwise, the end date will be set to the start date of the medication

Imputed medication date flag

If the year of the imputed date is not equal to the year of the original medication date then imputed date flag = Y, else if the month of the imputed date is not equal to the month of the original medication date then imputed date flag = M, else if the day of the imputed date is not equal to the day of the original medication date then imputed date flag = D, else imputed date flag = null. Imputed medication date flags will be created separately for both medication start and end dates.

9.2 Changes to protocol specified analyses

The definition of the ITT analysis set was changed from the protocol to the SAP and a mITT analysis set was introduced. In addition, the SAP specifies that the mITT analysis set will be used for the analysis of the primary endpoint and the ITT analysis set will be used for the analysis of all secondary efficacy endpoints.

The definition of the mITT analysis set is identical to the definition of the ITT analysis set in the protocol, ensuring that the population of patients entering the analysis of the primary endpoint remains as planned in the protocol.

The ITT analysis set was redefined in the SAP to remove the restriction of patients requiring a baseline and at least one post-baseline anti-Ab40 antibody assessment. This is to ensure that valid data from secondary endpoints are not excluded from the analysis, based on the availability of primary endpoint assessments.

Additional per-protocol analysis sets were introduced.

The Part A PPc Analysis Set comprising of all patients in the ITT Analysis Set who received all doses of study medication (on V1, V4, V7, V10, V13 and V18), have attended the safety visit after booster (V20), have no major protocol deviations that could affect the efficacy analyses or major protocol deviations that have been classified as “Use of disallowed concomitant medication”, relating to use of Anti-Alzheimer Disease medication.

The Part B PPc Analysis Set will comprise of all patients in the ITT Analysis Set who received all doses of study medication (on V1B, V4B, V7B, V10B, V13B and V18B in Part B), have attended the safety visit after booster (V20B in Part B), have no major protocol deviations that could affect the efficacy analyses or major protocol deviations that have been classified as “Use of disallowed concomitant medication”, relating to use of Anti-Alzheimer Disease medication.

The PPc Analysis Sets will be used for the sensitivity analysis of secondary efficacy endpoints relating to the assessment of cognition and quality of life, while the PP Analysis Sets will be used for the sensitivity analysis of the primary efficacy endpoint and secondary efficacy endpoints relating to the characterization of immune response and the assessment of disease biomarkers.

Level of anti-A β 40 antibodies in plasma has been added as a secondary outcome, to further characterize immune response.

Table 2-3 presents variables those were not analyzed by the Araclon or vendor:

Table 2-3 Variables not analyzed

Variables	Analyzed	
	Part A	Part B
Anti-A β 42 antibodies in plasma samples	No	No (not planned)
Antibody secreting cells	Yes	No
Peripheral blood cell subsets by immunophenotyping	No	No (not planned)
Cytokine-secreting cells	Samples from only a small number of patients were analyzed. Hence, data for this analysis will not be reported.	No (not planned)
CFS biomarkers (Tau, P-tau, neurofilament light and neurogranin)	Yes	No
Other A β peptide species in CSF	No	No

Both the quantification of the Levels of cytokines in plasma; IL-2, IL-4, IL-5, IL-6, IL-10, IL-13, IL-15, TNF- α and IFN- γ and the analysis of cytokine -secreting cells in plasma had the common objective of characterizing the immune response type. Therefore, it was decided to proceed only with the analysis of cytokine-secreting cells (Th1 and Th2 response) to minimize execution times and costs associated with the study. However, samples from only a small number of patients were analyzed. Hence, data for this analysis will not be reported.

9.3 Laboratory test parameters

Table 3-1 provides a listing of laboratory test parameters that will be recorded throughout the study and details of which parameters will be summarized descriptively.

Table 3-1 List of laboratory test parameters

Lab Category	Lab Sub-Category	Test Parameter	Summarize
Biochemistry	Electrolytes	CALCIUM / SERUM	Y
Biochemistry	Electrolytes	CHLORIDES / SERUM	Y
Biochemistry	Electrolytes	PHOSPHORUS / SERUM	Y
Biochemistry	Electrolytes	POTASSIUM / SERUM	Y
Biochemistry	Electrolytes	SODIUM / SERUM	Y
Biochemistry	Enzymes	ALKALINE PHOSPHATASE	Y
Biochemistry	Enzymes	ALT-SGPT	Y
Biochemistry	Enzymes	AST-SGOT	Y
Biochemistry	Enzymes	CREATINE KINASE	Y
Biochemistry	Enzymes	GAMMA-GT	Y
Biochemistry	Enzymes	LDH / SERUM	Y
Biochemistry	Substrates	ALBUMIN / SERUM	Y
Biochemistry	Substrates	APOLIPOPROTEIN E	Y
Biochemistry	Substrates	BLOOD UREA NITROGEN (BUN) / SERUM	Y
Biochemistry	Substrates	CHOLESTEROL	Y
Biochemistry	Substrates	C-REACTIVE PROTEIN / SERUM	Y
Biochemistry	Substrates	CREATININE / SERUM	Y
Biochemistry	Substrates	FERRITIN	Y
Biochemistry	Substrates	GLUCOSE / SERUM	Y
Biochemistry	Substrates	TOTAL BILIRUBIN / SERUM	Y
Biochemistry	Substrates	TOTAL PROTEIN / SERUM	Y
Biochemistry	Substrates	TRIGLYCERIDES	Y
Biochemistry	Substrates	UREA / SERUM	Y
Biochemistry	Substrates	URIC ACID / SERUM	Y
Coagulation		aPTT	Y
Coagulation		FIBRINOGEN	Y
Coagulation		HAEMOGLOBIN A1C	Y
Coagulation		INR	Y
Coagulation		PROTHROMBIN TIME	Y
Coagulation		RATIO	Y
Hematology		BASOPHILS	Y
Hematology		BASOPHILS %	Y
Hematology		EOSINOPHILS	Y
Hematology		EOSINOPHILS %	Y
Hematology		ERYTHROCYTES	Y
Hematology		HAEMOGLOBIN	Y
Hematology		HEMATOCRIT	Y
Hematology		LEUKOCYTES	Y
Hematology		LYMPHOCYTES	Y
Hematology		LYMPHOCYTES %	Y
Hematology		MCH	Y
Hematology		MCHC	Y
Hematology		MCV	Y
Hematology		MONOCYTES	Y
Hematology		MONOCYTES %	Y
Hematology		MPV	Y
Hematology		PDW	Y
Hematology		PLATELETS	Y
Hematology		RDW	Y
Hematology		TOTAL NEUTROPHILS	Y

Lab Category	Lab Sub-Category	Test Parameter	Summarize
Hematology		TOTAL NEUTROPHILS %	Y
Homocysteine		HOMOCYSTEINE	Y
Hormones		FREE T4 (FREE THYROXINE)	N
Hormones		TSH (THYROID-STIMULATING HORMONE)	N
Immunology		ANTI-NUCLEAR ANTIBODIES	N
Immunology		IMMUNOFLUORESCENT PATTERN	N
Immunology		NATIVE dsDNA ANTIBODIES	N
Immunology		Native dsDNA antibodies result	N
Immunology		THYROGLOBULIN ANTIBODIES	N
Immunology		TPO ANTIBODIES	N
Serology		HEPATITIS B SURFACE ANTIGEN (HBsAg)	N
Serology		HEPATITIS C ANTIBODIES	N
Serology		HUMAN IMMUNODEFICIENCY VIRUS, 4TH GENERATION TEST	N
Serology		RHEUMATOID FACTOR	N
Serology		RPR TEST	N
Serology		TREPONEMA PALLIDUM TOTAL ANTIBODIES	N
Urinalysis		Bacterial flora	N
Urinalysis		Calcium oxalate crystals	N
Urinalysis		Epithelial cells	N
Urinalysis		Erythrocytes	N
Urinalysis		Leukocytes	N
Urinalysis		Normal sediment	N
Urinalysis		Uric acid crystals	N
Urinalysis		BLOOD	N
Urinalysis		DENSITY	N
Urinalysis		GLUCOSE	N
Urinalysis		KETONE	N
Urinalysis		LEUCOCYTES	N
Urinalysis		NITRITES	N
Urinalysis		PH	N
Urinalysis		PROTEINS	N
Urinalysis		UROBILIN	N
Urinalysis		UROBILINOGEN	N
Vitamins		FOLIC ACID (FOLATE)	Y
Vitamins		VITAMIN B12	Y
